Primary data consist of biometric data collected during in-person screenings conducted by registered nurses and self-reported data gathered from PHA surveys. The biometric data includes blood pressure, height and weight (inputs into the calculation of BMI), and blood measurements of cholesterol and blood sugar. PHAs contain self-reported information on health behaviors. Unlike the administrative data, these primary data are available for individuals in the 25 treatment worksites and the 25 primary control worksites who completed the PHA and biometric data collection between 08/01/2017 and 10/31/2017.

B1. Biometric screening data

In the treatment and primary control worksites, we conducted biometric screenings after the conclusion of the last wellness module. The screenings were conducted by registered nurses in the worksites, who met with employees individually. We defined all of the following biometric outcomes as continuous variables.

- Total cholesterol
- High-density lipoprotein (HDL) cholesterol
- Blood glucose (mg/dl)
- Systolic blood pressure
- Body mass index (BMI): weight in kilograms divided by the square of height in meters

Table 5 provides summary statistics for biometric screening data from employees who were screened in the control worksites.

B2. Personal Health Assessment Data

At the conclusion of the wellness modules, we also fielded PHA surveys in each of the treatment and primary control worksites. Employees were asked to complete a paper survey with questions relating to their health behaviors, mental health, and general wellbeing. We use this dataset to assess the impact of the wellness program on employees' self-reported health behaviors and perceived health status.

Based on an examination of the distribution of PHA responses collected from the control group, we examine the following outcome variables.

- **Health behaviors:**

Screenings and Exams

- *Percent of recommended tests received:* We pooled commonly recommended tests (based on age and sex) covered in the PHA and determined the share of those tests that respondents reported obtaining. These tests are cholesterol level, fasting blood glucose level, blood pressure, dental exam, colon cancer screening, mammogram, and pap smear.

Physical activity

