The key identifying assumption is that the only mechanism through which being employed in a treatment worksite affects outcomes is through the availability of the wellness program. There are two threats to this assumption. First, to the extent that covariates were not balanced at baseline and those covariates affect the outcomes of interest, that imbalance could bias our estimates. We control for observed covariates and apply weights to balance covariates between treatment and control. Despite these adjustments, unobserved covariates might still be imbalanced.

Second, to the extent that the wellness program affected hiring or tenure of employees, their presence in the data set may be endogenously determined. We address the issue of endogenous entry by pre-specifying a subsample of those who were already employed at the time the intervention began. We defined this more restrictive “stable employment” subsample as comprising employees who had worked continuously for 13 weeks prior to the wellness program. This comes at a cost of reducing the overall sample size. Our goal in choosing the definition for this subsample was to balance the costs and benefits, as detailed in Appendix 2.

In this stably employed subsample, however, exit from the firm's workforce is still potentially endogenous. We deal with this concern in two ways. First, we will test balance on exit between treatment worksites vs. from control worksites overall and for subgroups. Indeed, tenure and time worked are among our primary outcomes. To the extent that we observe any unbalanced exit, we will perform a bounding exercise (assuming that those who exited have outcomes working against any observed effects of the intervention).

D. Subgroup analyses

We pre-specified three subgroup analyses. We selected these subgroups based on differences in key outcomes within the control group for those with different baseline characteristics, such as differences in medical spending by age or in reported exercise by sex (**Table 11**).

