Notes: The average participation rate for each module was calculated as the percentage of individuals who completed a module out of all who were eligible to complete a module during the time that the module was running. Participation is equivalent to completion of a module, with an incentive of a gift card for completion of the module. Descriptions of each module and their criteria for completion are provided in Appendix 1. Employees could only participate in the Take Charge of Your Health module once, though it was run twice. Club Cardio Challenge had two rounds and completion of either round 1 or round 2 earned a gift card; completion of both rounds did not earn an additional gift card, but rather an entry into a raffle for a Fitbit, unless the employee had Cigna health insurance, in which case they could complete both rounds of Club Cardio Challenge for an additional fitness reimbursement. Nutrition for a Lifetime occurred in two rounds; individuals who completed round 1 earned an ActivBAND or gift card. Completion of round 1 and round 2 earned an additional gift card or weight management reimbursement for Cigna members. Values were weighted by the number of days an individual was working during a given module's timeframe.

Panel B. Intensity of Participation by Definition

Definition of Participation	Employees at Treatment Worksites (N = 7288)	Participants at Treatment Worksites (N = 2071)
Completed any module (%)	28.4	100.0
Modules completed (#)	1.17	4.11
3 or more modules (%)	16.7	58.8

Notes: These summary statistics show the intensity of participation in the treatment group according to the 3 definitions of participation. In contrast to Panel A above, the sample (denominator) for these calculations was all employees at treatment worksites (first column) and all employees at treatment worksites who completed any module (second column) throughout the study period. Because of this difference in the denominators, participation rates for a given module in Panel A could exceed the average participation study-wide in Panel B.

Table 8: Balance Between Treatment and Control—Employee Level**Panel A.1: All Employees – Unweighted**

	(1)	(2)	(3)	(4)	(5)
	Treatment (n=7288)	Primary Control (n=7377)	Primary + Secondary Control (n=41376)	(1) vs (2) P value	(1) vs (3) P value
Demographics					
Age (yrs)	33.5	32.8	33.0	0.333	0.358
Female (%)	46.9	46.8	45.6	0.942	0.444
Race (%)				<0.001	<0.001
Black	21.1	25.2	26.7		
White	57.7	51.6	48.8		

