Employee Demographics					
Age (yrs)	38.5	37.6	38.1	0.165	0.458
Female (%)	48.3	46.6	45.7	0.348	0.065
Race (%)					
Black	17.6	19.4	20.4	0.723	0.463
White	65.6	60.0	57.2	0.427	0.098
Hispanic	11.4	16.1	16.6	0.321	0.150
Other	5.5	4.4	5.8	0.295	0.665
County-Level Demographics					
Age (yrs)	40.0	39.8	39.7	0.798	0.725
Female (%)	51.1	51.4	51.3	0.183	0.228
Race (%)					
Black	12.4	12.8	13.3	0.909	0.725
White	75.9	76.9	74.7	0.773	0.687
Hispanic	11.0	14.3	13.7	0.341	0.170
Other	11.7	10.2	12.0	0.396	0.833

Notes: Demographic characteristics are plausibly unaffected by the treatment. Employee demographics are taken from the Team Member database supplied by BJ's and based on the first entry for an individual during the treatment period. Age is defined as of December, 2014 (pre-treatment). ACS demographics are taken from the 2015 American Community Survey (ACS) Population Estimates for the county each worksite is located in. Worksite-level analyses are obtained by first calculating a weighted average for each worksite (weighted by an employee's hours worked during the treatment period). Column 1 reports the means for employees in the treatment group while columns 2 and 3 report the means for the primary control employees and all control employees (primary and secondary), respectively. Treatment status is defined by the first worksite an employee appears in during the treatment period. Column 4 reports the p-value for the comparison between the employees at treatment worksites and the employees at primary control worksites and column 5 reports the p-value for the comparison between the employees at treatment worksites and all employees at control worksites.

Table 10: First Stage Estimates

Panel A: Employee Level—All

	All		Completed PHA		Cigna Enrolled	
	(1) Control Mean	(2) Estimated First Stage	(3) Control Mean	(4) Estimated First Stage	(5) Control Means	(6) Estimated First Stage
Completed any module (%)	0.21	27.53 (1.25) [0.00]	2.29	63.06 (1.98) [0.00]	0.91	57.31 (2.81) [0.00]
Modules completed (#)	0.01	1.12 (0.09) [0.00]	0.08	3.45 (0.24) [0.00]	0.03	3.13 (0.26) [0.00]
3 or more modules (%)	0.12	15.95 (1.08) [0.00]	1.60	46.74 (2.31) [0.00]	0.53	43.29 (2.74) [0.00]
Average total incentive payment (\$)	0.26	37.97 (3.20) [0.00]	3.20	126.54 (9.40) [0.00]	1.37	148.83 (11.93) [0.00]
N	41,376	48,664	1,454	2,793	7,174	8,559

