Note: Control means and first stage estimates of the impact of TREATMENT on alternate definitions of PARTICIPATION. All regressions include demographic and employment controls (age, sex, age-sex interactions, race/ethnicity, full-time status, paid hourly status, and job category) and cluster standard errors at the worksite level. All samples other than the sample with Cigna coverage also include a control for whether or not the employee ever had Cigna coverage during the treatment period. Employee-level regressions are weighted by a weight that balances treatment and control on demographic characteristics. Standard errors shown in parenthesis and p-values in brackets.

Panel B: Employee-level—Stably Employed Sub-sample

	All		Surveyed		Cigna	
	(7) Control Mean	(8) Estimated First Stage	(9) Control Mean	(10) Estimated First Stage	(11) Control Means	(12) Estimated First Stage
Completed any module (%)	0.57	49.75 (2.82) [0.00]	3.90	79.22 (2.74) [0.00]	0.97	59.54 (3.24) [0.00]
Modules completed (#)	0.02	2.56 (0.21) [0.00]	0.15	5.41 (0.39) [0.00]	0.04	3.41 (0.29) [0.00]
3 or more modules (%)	0.35	35.04 (2.47) [0.00]	2.96	67.78 (3.39) [0.00]	0.61	45.79 (3.15) [0.00]
Average total incentive payment (\$)	0.75	97.62 (8.45) [0.00]	5.92	217.91 (15.74) [0.00]	1.54	163.36 (13.80) [0.00]
N	13,000	15,344	747	1,396	5,779	6,907

Note: Control means and first stage estimates of the impact of TREATMENT on alternate definitions of PARTICIPATION. All regressions include demographic and employment controls (age, sex, age-sex interactions, race/ethnicity, full-time status, paid hourly status, and job category) and cluster standard errors at the worksite level. All samples other than the sample with Cigna coverage also include a control for whether or not the employee ever had Cigna coverage during the treatment period. Employee-level regressions are weighted by a weight that balances treatment and control on demographic characteristics. Standard errors shown in parentheses and p-values in brackets.

Panel C: Worksite level

	All		Surveyed		Cigna	
	(1) Control Mean	(2) Estimated First Stage	(3) Control Mean	(4) Estimated First Stage	(5) Control Means	(6) Estimated First Stage
Completed any module (%)	0.22	28.19 (1.27) [0.00]	3.07	62.25 (1.89) [0.00]	0.91	57.29 (2.83) [0.00]
Modules completed (#)	0.01	1.17 (0.09) [0.00]	0.11	3.49 (0.22) [0.00]	0.03	3.18 (0.27) [0.00]
3 or more modules (%)	0.12	16.69 (1.12) [0.00]	2.27	46.65 (2.16) [0.00]	0.54	43.68 (2.76) [0.00]

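### PHA and biometric outcomes are analysed in completers only, treated PHA completers are strongly enriched for program participants, and no planned safeguard is specific to non-completion among current staff

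*Combined protocol and SAP*

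**What the plan says.** Section IV.B takes the biometric and Personal Health Assessment (PHA) data from employees of the 25 treatment and 25 primary control worksites "who completed the PHA and biometric data collection between" 1 August and 31 October 2017. Tables 5 and 6 are built on these people.

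Three safeguards bear on who is in the data:
- Section V.B weights the arms to agree on age, sex and race.
- Equation (1) in Section VI.A adds demographic and job covariates and time worked. The notes to Tables 5 and 6 add Cigna coverage.
- Sections V.A and VI.C deal with people leaving the firm: "To the extent that we observe any unbalanced exit, we will perform a bounding exercise".

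Section VI.C names two threats, covariate imbalance and effects of the program on hiring or tenure. Non-completion by staff who are still employed is not among them.

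Table 10 reports the first stage for completing any module. In all employees it reads "27.53 (1.25) [0.00" and in PHA completers "63.06 (1.98) [0.00". In the stably employed it reads "49.75 (2.82) [0.00" overall and "79.22 (2.74) [0.00" among those surveyed.

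**The concern.** Randomization protects a comparison of everyone assigned. It does not protect a comparison of those who chose to attend a survey and screening almost three years later, if the program itself affected who attended. That is plausible here. Section II lists the PHA and the screenings as components of the program, and it places a dietitian in each treatment worksite for about 8 hours a week to engage staff. Control worksites had the data collection without that contact.

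If treated completers include more health-minded people than control completers, self-reported exercise or weight management could differ between arms with no program effect. The introduction says that these are the kinds of outcome that were significant in phase 1. The enrichment of treated completers for participants is the visible sign that completion and engagement go together in the treatment arm.

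**Working it through.** **1. The plan's own figures.** Table 7 Panel B has columns headed "Employees at Treatment Worksites (N = 7288" and "Participants at Treatment Worksites (N = 2071". 2,071/7,288 = 28.4%; 0.2842 × 4.11 = 1.17 modules; 0.2842 × 58.8% = 16.7%. All agree with the table. Treated PHA completers from Table 10 are 2,793 − 1,454 = 1,339, as in Table 8 Panel B. In the stably employed they are 1,396 − 747 = 649.

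**2. Treated levels.** Table 10 gives differences, so treated level = control mean + first stage (regression-adjusted, hence approximate).

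| Sample | Any module, % | Modules, number |
|---|---|---|
| All | 0.21 + 27.53 = 27.7 (28.4 raw) | 0.01 + 1.12 = 1.13 (1.17 raw) |
| PHA completers | 2.29 + 63.06 = 65.4 | 0.08 + 3.45 = 3.53 |
| Stably employed, all | 0.57 + 49.75 = 50.3 | 0.02 + 2.56 = 2.58 |
| Stably employed, surveyed | 3.90 + 79.22 = 83.1 | 0.15 + 5.41 = 5.56 |

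The ratio for any module is 65.4/28.4 = 2.3 overall and 83.1/50.3 = 1.65 in the stably employed.

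**3. The same contrast as completion.** Participants among treated completers: 0.6535 × 1,339 = 875. So 875/2,071 = 42% of participants completed the PHA, against 464/5,217 = 9% of non-participants. These denominators are everyone ever employed, so the figures mix leaving the firm with not responding. They are not response rates.

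**4. How much could be tenure?** Completers had to be on staff in late 2017 and so had more modules open to them. Two checks in the stably employed:
- The twelve eligible-at-the-time module rates in Table 7 Panel A sum to 3.43. Surveyed stable employees average 5.56, a ratio of 1.6. This is only indicative, since long-stayers may participate at above-average rates.
- If response were unrelated to participation, retention would have to be r1 = 0.8312 × S/0.5032 in participants and r0 = (S − 0.5032 × r1)/0.4968 in non-participants, where S is overall retention. Appendix 2 gives 51% for controls at the end of 2017. Applying that to treated staff is an assumption. S = 0.51 needs 84% and 17%; S = 0.60 needs 99% and 20%.

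Tenure explains part of the gap, but does not readily explain all of it.

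**5. Completion by arm.** Treated 1,339/7,288 = 18.4%; primary control 1,336/7,377 = 18.1%. Table 10 counts 1,454 control completers, 118 more than Table 8. Its Panel C lists 85 surveyed control worksites, so the extra people may have started at secondary control sites (an inference). In the stably employed, treated completion is 649/2,344 = 27.7%. Control is at most 747/2,378 = 31.4%, or (747 − 118)/2,378 = 26.5% if all 118 belong to that group.

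**6. Possible size, illustration only.** Bias = (0.6535 − p) × D. Here p is the share of control completers who would have participated, and D is the underlying outcome gap between participants and non-participants. Neither is in the documents. For D = 10 percentage points, p from 0.284 to 0.60 gives 3.7 down to 0.5 points; with D from 5 to 20 the range is 0.3 to 7.4. At p = 0.6535 it is zero. For comparison, the standard error for regular exercise is 100 × √[0.5379 × 0.4621 × (1/1,339 + 1/1,440)] = 1.9 points without clustering. With an assumed intracluster correlation of 0.01 to 0.02 (design effect 1.53 to 2.05 at 53.6 completers per site) it is 2.3 to 2.7.

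**The case against.** The strongest reply is that enrichment for participants is not differential selection. Control employees could not complete modules, apart from the few who changed sites, but control completers also chose to attend. If the same motivated people come forward in both arms, treated completers will be full of participants and the comparison is still fair. A reader might infer from Table 10 that the treated arm has a filter that controls lack. The documents do not support that, because would-be participants among controls are unobserved. This reply stands, and it limits the point to a risk.

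Three more readings go too far. The 63 and 79 in Table 10 are adjusted differences and not shares of treated completers. The contrast of 65% with 28% is not survey selection alone, because the 28% covers anyone employed at any time in 36 months. And the plan is not without adjustment: the weights and covariates remove measured demographic and job differences, Section V.B reports job characteristics balanced in all subsamples, and it concedes that unobserved differences may remain.

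The near-equal completion shares and the demographic balance in Table 8 Panel B reassure less than they seem to. Equal shares can hide different people. The shares use everyone ever employed, whereas the note to Figure 2 uses staff working in the window (the percentages are in a figure that is not shown here). Panel B is weighted on the same demographics that it displays.

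**Conclusion.** The point holds as a gap in the plan and not as a demonstrated bias. Tables 5 and 6 rest on completers, treated PHA completers are strongly enriched for participants (about 65% against 28%, and 83% against 50% in the stably employed), and the only bounding planned concerns exit from employment. Whether selection differs by arm cannot be settled from the documents, and neither the size nor the sign of any bias can be derived from them. Under the assumed values above, it could lie anywhere from zero to more than one standard error of a PHA outcome. Extending the point to the biometrics is an inference from the shared data collection, since Table 10 gives participation for PHA completers only. It matters because a difference in self-reported behavior could otherwise be read as a program effect without any check on response.

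**What to change.** Work among staff of the 50 worksites employed from 1 August to 31 October 2017. The note to Figure 2 ends the window on 30 October, so state one date.

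1. Fit a response model in each arm on variables held in both: age, sex, race, job type, full-time status, tenure or time worked, Cigna coverage and absenteeism. Multiply the inverse response probabilities into the balance weights, and report response-weighted versions of Tables 5 and 6 beside the base results. Modules completed may enter the treated-arm model only as a further, labelled sensitivity analysis. It has no control counterpart and could create the imbalance that it is meant to remove.
2. Re-estimate the ITT for absenteeism, and for spending in Cigna members, in completers. Compare it with all window-employed staff of the same sites, not with everyone ever employed, which would confuse response with tenure. If the two differ, report Tables 5 and 6 as subject to response selection.

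Trimming bounds are not a substitute. At the completion shares above they would trim 1 − 18.11/18.37 = 1.4%, and they address a difference in rates, not in composition.

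The administrative data are already held. The cost is analysis time and somewhat wider intervals. Response weights correct only for measured differences, so agreement in step 2 would be supportive but not conclusive.

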The wellness program took place in 2 phases. Phase 1 of the treatment period spanned 18 months, from January 2015 through June 2016. In phase 2 of the study, the treatment period was extended for another 18 months, from January 2015 through December 2017 and is the focus of this analysis plan (**Table 1**). In phase 2, 5 additional treatment worksites and 5 additional primary control worksites were added to the experiment. This wellness program was designed and implemented by a third-party vendor, Wellness Workdays. Wellness Workdays is a wellness vendor that delivers and manages wellness programs across many industries, including finance, manufacturing, banking, higher education, and legal across a number of states.

The wellness program consisted of a personal health assessment (PHA), in-person screenings, and multiple program modules. Each module took place over 4-10 consecutive weeks. The modules centered on themes such as team-based and individual wellness challenges, nutrition, stress reduction, and physical activity, as well as workplace culture. For each module, participants could earn modest financial rewards (\$25-50) for completion.

The 3-year intervention period comprised 12 modules. Eight modules were offered during the first 18 months (phase 1): "Take Charge of Your Health," which taught proactive strategies for participating in health and health care; "Nutrition for a Lifetime," which aimed to help employees achieve and maintain a healthy weight through nutrition; "Club Cardio Challenge" (consisting of 2 modules), which focused on cardiovascular activity; "Maintain Don't Gain," which combined principles of healthy nutrition with physical activity; "Power Down the Pressure," which taught methods for stress management; "Weight Loss Boot Camp," which

focused on nutrition and exercise methods for weight loss; and “Movin’ in May,” which once again focused on physical activity with active tracking of progress.

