Among these worksites, we randomly selected 25 “treatment” worksites that would receive the wellness program and 25 “primary control” worksites for phase 2.⁵ These primary control worksites participated in data collection through PHAs and in-person biometric screenings, but did not receive the wellness program treatment. **Figure 1** shows the locations of the 25 treatment and 25 control worksites across the Eastern U.S. The remaining 110 worksites served as “secondary controls.” which were included in analyses of administrative data. Thus, the primary data described below was collected from the 50 treatment and primary control worksites; administrative data were compiled for all 160 worksites. **Figure 2** shows a Consolidated Standards of Reporting Trials (CONSORT) flow diagram for our phase 2 evaluation, including the sample sizes of treatment and control groups.

⁵ For the first 18 months of the study (phase 1), there were 20 treatment and 20 primary control sites.

Randomization at the worksite level allows us to assess the effects of interventions that aim to affect workplace culture or operate on a group level, such as using common break rooms to stage nutrition demonstrations, team-based activities, or worksite level prizes.

IV. Data

Our analysis focuses on outcomes from five data categories. The Table below displays the source of each data set and the study population from which it is derived.

Summary of the Components of Data Collected				
Data	Source	Treatment Worksites (25)	Primary Control Worksites (25)	Secondary Control Worksites (110)
Administrative Data				
Employment records	BJ's	All employees	All employees	All employees
Claims data (medical and pharmaceutical)	Cigna (via BJ's)	Employees insured by Cigna	Employees insured by Cigna	Employees insured by Cigna
Primary Data				
Biometric screening data	Wellness Workdays	Employees completing screening	Employees completing screening	None (by design)
Personal Health Assessment	Wellness Workdays	Employees completing survey	Employees completing survey	None (by design)
Participation in the treatment	Wellness Workdays	All employees	None (by design)	None (by design)

A. Administrative Data

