	Program announced						Registered Dietitians begin working in the treatment worksites																													
Year	2015												2016												2017											
Month	1	2	3	4	5	6	7	8	9	10	11	12	1	2	3	4	5	6	7	8	9	10	11	12	1	2	3	4	5	6	7	8	9	10	11	12
Program Announcement	█																																			
Module 1. Take Charge of Your Health Round 1 & 2		█	█	█	█																															
Module 2. Nutrition for a Lifetime						█	█																													
Module 3. Club Cardio Challenge Round 1								█	█																											
Module 4. Club Cardio Challenge Round 2										█	█																									
Module 5. Maintain Don't Gain												█																								
Module 6. Power Down the Pressure														█																						
Module 7. Weight Loss Boot Camp																█																				
Module 8. Movin' in May																	█																			
Surveys and Biometrics																		█	█																	
Module 9. Healthy and Fit																				█	█															
Module 10. Nutrition for a Lifetime Round 1																					█	█														
Module 11. Nutrition for a Lifetime Round 2																						█	█													
Module 12. Step Challenge																														█	█					
Surveys and Biometrics																																			█	█

Notes: This table presents a graphical illustration of Phase 1 and Phase 2 of the wellness programs. The treatment began in 2015 with announcements of the wellness program worksite assignments (treatment worksites) in January followed by administration of the personal health assessments (PHAs) and in-person screenings in February. Phase 1 comprised 8 modules and concluded at the end of June 2016. After Phase 1, PHAs and in-person screenings were conducted during the summer of 2016. Afterwards, Phase 2 of the wellness program began in the fall of 2016, with PHAs and in-person screenings in fall of 2017.

Table 2. Summary of Demographic Characteristics for Employees in Control Worksites

	Employee-level			Stably Employed Subsample			Worksite-level		
	All	PHA	Cigna	All	PHA	Cigna	All	PHA	Cigna
Age (yrs)	34.5	39.8	45.3	39.6	44.3	45.3	39.4	42.4	45.2
Female (%)	47.2	56.9	45.6	47.0	62.5	45.9	46.2	57.6	45.8
Race (%)									
White	52.0	57.4	69.1	60.2	60.7	68.0	58.7	59.0	68.5
Black	25.9	19.1	14.4	19.0	14.6	15.0	20.7	18.2	14.5
Hispanic	16.7	17.8	13.4	17.3	19.6	14.0	16.4	17.7	14.1
Other race	5.4	5.6	3.1	3.5	5.1	3.1	4.1	5.1	2.9
Employment (%)									

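### The recommended-tests index can include cholesterol, blood pressure and possibly glucose tests given by the trial itself, so it needs component rows before it is read as care obtained elsewhere

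*Combined protocol and SAP*

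**What the plan says.** Section IV.B2 (Screenings and Exams) pools tests recommended by age and sex and "determined the share of those tests that respondents reported obtaining". The list reads: "These tests are cholesterol level, fasting blood glucose level, blood pressure, dental exam, colon cancer screening, mammogram, and pap smear". No look-back period, place of testing or exclusion of trial-provided tests is stated.

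Section IV.B describes the trial's own measurements: "The biometric data includes blood pressure, height and weight (inputs into the calculation of BMI), and blood measurements of cholesterol and blood sugar". Section IV.B1 says where and when: "In the treatment and primary control worksites, we conducted biometric screenings after the conclusion of the last wellness module". Both the survey (PHA) and the biometric data come from 1 August to 31 October 2017.

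Screening has two roles in the plan. Section II makes it part of the intervention: "The wellness program consisted of a personal health assessment (PHA), in-person screenings, and multiple program modules". Section III makes it data collection for primary control sites, which "participated in data collection through PHAs and in-person biometric screenings, but did not receive the wellness program treatment". The Table 1 notes add a round in summer 2016 and mention PHAs and screenings in February 2015.

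**The concern.** A respondent who truthfully reports a cholesterol or blood pressure test may be reporting the one that the trial's nurse performed. Module 1 taught which routine tests to have and how often, so a reader will naturally take this outcome as evidence on whether the program leads employees to obtain recommended care.

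Counted on-site tests disturb that reading in two ways. If both arms count them equally, those items are already ticked and a real effect is diluted. If one arm counts them more, the index differs between arms although nobody sought more care. Either way, the pooled index alone cannot separate care obtained elsewhere from the trial's own measurements.

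**Working it through.** The plan gives no power or precision figure for this outcome, so there is none to reproduce. The checks below ask how large the overlap is and what the tabulated figures allow.

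**1. Overlap in items.** Cholesterol and blood pressure match directly. The index specifies fasting glucose, while the on-site measure is listed only as blood glucose. So k = 2 or 3 of 7 items overlap. The age and sex rules are not given, so I assume a respondent is due between d = 4 (cholesterol, glucose, blood pressure, dental) and d = 7 tests. The overlapping share k/d is:

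| | d = 7 | d = 4 |
|---|---|---|
| k = 2 | 29% | 50% |
| k = 3 | 43% | 75% |

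**2. Overlap in people.** Control counts from Table 5, divided by the 1,454 control respondents for the index in Table 6:
- cholesterol 1,392/1,454 = 95.7%
- glucose 1,390/1,454 = 95.6%
- systolic blood pressure 1,400/1,454 = 96.3%

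If those screened are PHA respondents, nearly all respondents were screened in the same window.

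**3. Were all the on-site tests counted?** Table 6 gives a control mean of 58.00 and an SD of 32.51. Suppose 95.6% had all three tests counted and all three are in everyone's denominator. Each of these respondents then scores at least 3/7, the most lenient floor. The SD is largest with the other 4.4% at 0, a share x at 3/7 and a share y at 1:
- x + y = 0.956 and (3/7)x + y = 0.58 give x = 0.376/0.571 = 0.658 and y = 0.298
- variance = 0.658 × 0.1837 + 0.298 − 0.58² = 0.0825, so the largest SD is 28.7

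That is below 32.51, so full counting of three tests does not fit. At this floor, the share counting all three can be at most about 90%. Two counted tests (floor 2/7) allow an SD up to 36.9, so partial counting is not excluded. The bound is approximate because the Table 6 SDs may be weighted.

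**4. Equal counting.** Assume a share c = 0.5 of each arm counts the on-site tests, regardless of care elsewhere, and a true effect of 5 points on every item. The observed effect is 5 × (1 − c·k/d):
- k = 3: 5 × 0.625 = 3.1 points (d = 4); 5 × 0.786 = 3.9 points (d = 7)
- k = 2: 5 × 0.75 = 3.75 points (d = 4); 5 × 0.857 = 4.3 points (d = 7)

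**5. Unequal counting.** Let δ be the excess of treated over control respondents counting an on-site test, and p the share of them already tested elsewhere. The shift is δ(1 − p)k/d. With δ = 10 points and p = 30% to 70%, all assumed:
- k = 3: 10 × 0.3 × 3/7 = 1.3 to 10 × 0.7 × 3/4 = 5.3 points
- k = 2: 10 × 0.3 × 2/7 = 0.9 to 10 × 0.7 × 2/4 = 3.5 points

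Higher final-round attendance in the treatment arm could not produce δ = 10. With controls at 95.6% or more, the room is 100 − 95.6 = 4.4 points, giving at most 4.4 × 0.7 × 3/4 = 2.3 points. For scale, the unclustered standard error is 32.51 × √(1/1,454 + 1/1,339) = 1.23 points, with 1,339 = 2,793 − 1,454 from Table 10. The plan clusters by worksite, so the actual standard error may be larger.

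**The case against.** The strongest reply is that the documents show an overlap of test types, not that the index contains trial tests. The PHA item wording and look-back are not given. Neither is the order of survey and screening within the window: if the paper survey came first, the final screening could not have been reported. The glucose items may not match, and the Table 6 SD speaks against full counting. All of this stands and limits the point to what the index can include. It does not remove the point, because the summer 2016 round came before the final PHA whatever the order in 2017, and partial counting fits the tabulated figures.

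A reader might go further and infer that the treatment arm was screened more often, so that the index is biased in the program's favour. The Table 1 note on February 2015 invites this: assignments were announced, "followed by administration of the personal health assessments (PHAs) and in-person screenings in February". But the sentence does not say which arms were screened, the Table 1 grid shows no such round, and the look-back is unknown. The sites added at month 18 split 5 and 5, so fewer rounds there need not unbalance the arms.

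It can also be said that the plan never defines the index as care obtained outside the trial. It uses the PHA for self-reported behaviors and perceived health, and screening is itself a program component. This is fair, and it is a reason to keep the pre-specified index and limit only the interpretation.

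**Conclusion.** The concern holds as a matter of interpretation. Two or three of the seven items can be satisfied by the trial's own screening in both surveyed arms, and nothing in the definition separates those tests from care obtained elsewhere. Neither an effect nor its absence on the pooled index can be read cleanly as an effect, or lack of one, on care outside the trial.

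Dilution is the more likely consequence, because both arms were screened. It would reduce an assumed 5-point effect to 3.1 to 4.3 points if half of each arm counted the on-site tests. A spurious effect needs unequal counting, which the documents do not establish. It would be tempting to conclude that the index simply measures attendance at the trial's screenings, but the Table 6 mean and SD argue against that.

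Severity is minor to moderate: this is one of 13 self-reported outcomes in Table 6, alongside the claims, biometric and employment outcomes. Confidence is medium. The overlap and the missing rule are plain, but actual counting is not shown.

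**What to change.** Keep the seven-item index as pre-specified. In Section IV.B2 and Table 6, add two pre-specified component rows:

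- (a) tests the trial does not perform: dental exam, colon cancer screening, mammogram and pap smear
- (b) cholesterol, glucose and blood pressure, labelled as possibly including on-site trial screening

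State that an effect, or lack of effect, on recommended care obtained outside the trial will be concluded only with support from (a). It would also help to state the PHA item wording, any look-back period, the order of survey and screening, and which arms had each round.

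The cost is a few sentences and two table rows. No new data are needed if the item-level PHA answers were kept. The plan says that treatment and control outcomes over the three years have not yet been compared, so the rows can still be pre-specified.

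The downside is precision: (a) has fewer items, only dental for some respondents, and is noisier. In the Table 11 regular-exercise counts, 744 of 1,440 control respondents are under 40 and 627 are men, so short item lists may be common. This is a further reason to add (a) beside the full index and not to replace it.
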